**Project Title: Exploration of responses to compassion in a clinical population**

**NCT number: TBC**

**Date: 20th March 2018**

### **Project executive summary**

This project focuses on exploring responses to compassionate imagery, a technique from Compassion Focused Therapy (CFT; Gilbert, 2014). Evidence has documented that CFT decreases depression, shame, self-criticism and increases self-esteem (Kirby, 2016). Compassion-focused imagery (CFI) is a key technique in CFT, which involves visualizing compassion towards others, or imagining people, places or objects directing compassion towards oneself. Single trials of CFI have shown a reduction of negative affect and physiological changes associated with the attenuation of threat-focused behaviors (e.g. Rockliff et al., 2008). Regular CFI practice has increased self-compassion and reduced negative affect in both clinical and non-clinical populations (Gilbert & Irons, 2004; McEwan & Gilbert, 2016). Unfortunately, CFI can create threat-focused responses in some individuals. However, these findings have been based on tasks involving receiving compassion from others.

The present study therefore aimed to explore participants' responses to imagery exercises involving self-compassion, in comparison to a relaxation task (to control for certain task demands but without the compassion element), and a control task ( reading a magazine).

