### **METHODS**

### Participants and process of recruitment:

We plan to recruit a sample of 25 participants for this study, based upon other studies of compassionate imagery with similar designs (Rockliff et al., 2008; Duarte et al., 2015).

Inclusion criteria are:

1. Clinical level of anxiety or depression (defined for this study  $\geq 8$  on the OASIS or ODSIS)
2. High self-criticism (we selected a cut-off of 0.5 standard deviations above the mean in self-inadequacy or self-hatred on the FSCRS). Based upon a validation in Colombia of the FSCRS by Naismith, Duran Ferro, Ingram, & Jiménez Leal (Submitted), this represents  $\geq 24$  in self-inadequacy or  $\geq 8$  in self-hatred.

These criteria were selected because these interventions are designed to help a clinical population presenting with high self-criticism. Offering this to a non-clinical population (i) reduces the likelihood of observing significant changes, and (ii) will not allow us to help those who present with higher needs.

Nonetheless, those who complete the initial screening and do not meet inclusion criteria will be invited to a group session to learn compassion techniques. They will also receive compassion materials via email at the end of the study.

For recruitment, posters will be hung inside the campus of the University of the Andes. The same information will be published in university social media pages.

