### Measures:

See Appendix 2 for copies of the questionnaires that we intend to use that are not validated.

- 1. Demographics**
- 2. Self-report form – Physiological variation**
- 3. Overall Depression Severity and Impairment Scale (ODSIS)**
- 4. Overall Anxiety Severity and Impairment Scale (OASIS)**
- 5. Forms of Self-Criticism/Attacking and Self-Reassuring Scale (FSCRS)**
- 6. Positive and negative affect generated**

**7. Heart Rate Variability (HRV).** Heart rate variability (HRV) is a physiological measure that allows us to quantify small changes in anxiety moment by moment, that a questionnaire cannot quantify. In this study it will allow us to measure whether participants respond to compassion with a threat-based response or a relaxed response (we expect that after 3-4 trials, all participants will respond with relaxation or a neutral response, but we predict that at the start, some will respond with threat-based responses).

We will use the BioPac system to collect HRV data. Electrodes will be placed using the Lund guidance which is considered the most stable, least invasive, and with high diagnostic accuracy. Using the program Acqknowledge, we will analyse beats per minute (BPM) and ratios of sympathetic and parasympathetic activity. Specifically, we will use the Root Mean Square of the Successive Differences (RMSSD) of RR intervals (Task Force of the European Society of Cardiology and the North American Society of Pacing and Electrophysiology, 1996). RMSSD was selected because there is no agreed clinically-significant change value for analysing HF HRV data (see Data analysis section).

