#### **Data analysis**

Paired *t*-tests will be run (i) to estimate differences in HRV during the self-compassion imagery, relaxation imagery and the control task, (ii) to examine changes in self-reported positive and negative affect from pre-CFI to post-CFI, (iii) to explore whether changes in positive and negative affect during CFI are greater or smaller from Trial 1 to Trial 3.

To complement group-level analyses, we will use reliable and clinically-significant change analyses. We will firstly report how many participants show a reliable change (Jacobson & Truax, 1991) in positive or negative affect following CFI.

We will also calculate how many individuals show a clinically-significant HRV response ( $\geq 5$ ms change in RMSSD within one individual between two different tasks).

Finally, we will report the number of positive and negative clinically-significant responses for both relaxation and compassion in each trial, in order to (i) compare effects of compassion versus relaxation at trial 1, and (ii) explore whether repeated trials improved response to each task.

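### The HRV responder counts name no reference task or sign and are not cross-classified within person, so they cannot show whether a negative response is specific to compassion

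*Combined protocol and SAP*

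**What the plan says.** The Project executive summary explains why relaxation is included: "to control for certain task demands but without the compassion element". The Procedure section has every participant do magazine reading, relaxation imagery and compassion-focused imagery (CFI) in each session, always in that order. Under Measures, the HRV item says that "it will allow us to measure whether participants respond to compassion with a threat-based response or a relaxed response", and it predicts that some participants will show threat at the start.

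The Data analysis section uses HRV at two levels.

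- Group level: paired t-tests "to estimate differences in HRV during the self-compassion imagery, relaxation imagery and the control task".
- Individual level: a response is a "change in RMSSD within one individual between two different tasks" of at least 5 ms. The plan will then "report the number of positive and negative clinically-significant responses for both relaxation and compassion in each trial", first to "compare effects of compassion versus relaxation at trial 1" and second to see whether repetition improves the response to each task.

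The section does not say which task is the reference, which direction is negative, or how the two sets of counts are to be compared. It plans no table of CFI response by relaxation response. The sample size rests on precedent: "We plan to recruit a sample of 25 participants for this study, based upon other studies of compassionate imagery with similar designs". No SD of RMSSD, or of its change between tasks, is given.

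**The concern.** The prediction that some participants respond to compassion with threat is a claim about individuals, and the responder counts are the part of the HRV analysis that addresses individuals. Relaxation can separate a reaction to compassion from a reaction to imagery in general only if the two responses are read together in the same person. Two separate totals drop that link.

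The missing reference task adds to the problem. If control is the reference, a person whose RMSSD falls by at least 5 ms in both imagery tasks enters the compassion negative count, although the fall may reflect imagery as such or a high control reading. If CFI is scored directly against relaxation, that person need not count as negative, but someone well above control in both tasks, and 5 ms lower in CFI than in relaxation, would. The two readings produce different lists of negative responders, and the plan leaves the choice open until the data are seen.

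**Working it through.** The plan states no power, alpha, SD or expected response rate on this point, so there is no figure to reproduce.

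**1. What separate totals leave open (no distributional assumption).** Let each task have k negatives among N = 25. The number negative on both lies between max(0, 2k − 25) and k, and the number negative on compassion only is k minus that overlap.

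- k = 5: overlap 0 to 5, compassion only 5 to 0.
- k = 8: overlap 0 to 8, compassion only 8 to 0.
- k = 10: overlap 0 to 10, compassion only 10 to 0.

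**2. Precision of the paired comparison.** Let b be negative on CFI only and c negative on relaxation only. The difference in proportions, (b − c)/25, follows from the totals. Its standard error, √[(b + c) − (b − c)²/25]/25, does not. Take totals of 10 (CFI) and 5 (relaxation) as an illustration, a difference of 5/25 = 0.20.

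- Overlap 5: b = 5, c = 0. SE = √(5 − 1)/25 = 0.08. Exact McNemar p = 2 × (1/2)⁵ = 0.0625.
- Overlap 0: b = 10, c = 5. SE = √(15 − 1)/25 = 0.15. Exact McNemar p = 2 × 4944/32768 = 0.30.

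The same two totals give standard errors that differ almost twofold.

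**3. Overlap if control is the reference (assumptions, not figures from the plan).** Treat CFI − control and relaxation − control as bivariate normal with mean zero and common SD. Correlation 0.5 is what equal, independent noise in the three recordings gives, because both differences use the same control reading. Negative means a change of −5 ms or lower. Then P = Φ(−5/SD), J is the joint probability that both are negative, and the share is J/P. Shares and counts come from unrounded values. With independent differences the share would simply be P.

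| SD (ms) | P | CFI negatives of 25 | J | Share also negative on relaxation | Share if independent | CFI only, 25 × (P − J) |
|---|---|---|---|---|---|---|
| 5 | 0.159 | 4.0 | 0.063 | 39% | 16% | 2.4 |
| 7 | 0.238 | 5.9 | 0.112 | 47% | 24% | 3.1 |
| 10 | 0.309 | 7.7 | 0.163 | 53% | 31% | 3.6 |
| 15 | 0.369 | 9.2 | 0.213 | 58% | 37% | 3.9 |

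The correlation adds about 21 to 23 percentage points over independence. Over a wider range (SD 5 to 20 ms, correlation 0.3 to 0.8) the share runs from 29% to 75%.

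**4. A general imagery effect.** Suppose both imagery tasks lower RMSSD by 5 ms against reading and compassion adds nothing. Then P = 0.50 and, at correlation 0.5, J = 1/3. That gives 12.5 CFI negatives, of whom 25/3 = 8.3 (67%) are negative on relaxation too and 12.5 − 8.3 = 4.2 are negative on CFI only.

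**5. The direct CFI − relaxation change.** Its variance is 2 × SD² × (1 − 0.5) = SD², and any shift common to both imagery tasks cancels. In the scenario of step 4 the expected number at −5 ms or lower is therefore the 4.0 to 9.2 in the third column, not 12.5. It removes the general imagery effect and the shared control reading, but not recording noise.

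**The case against.** The strongest reply is that the plan already compares the tasks within person. A reader might infer that compassion and relaxation are never linked in the same individual. The paired HRV t-tests contradict that: a compassion-relaxation pairing is a within-person comparison and does not use the control reading at all. The gap is confined to the responder counts, which the plan presents as a complement to the group analysis. This part of the reply stands, but a mean difference does not identify who reacts to compassion.

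A second reply is that totals of 8 and 8 do not give opposite answers to Objective 1, as a reader might infer. This is also right. Equal totals force b = c, so the discordant comparison is 0 v 0 or 8 v 8, a null difference either way. What the totals lose is the identity of the responders and the precision of the difference.

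Third, the miscount is conditional. A reader might infer that anyone who falls in both tasks is counted as a threat response. That follows only if control is the reference and the fall reaches 5 ms in CFI. The Data analysis section speaks of negative responses; threat is an inference, though a fair one, from the HRV item under Measures and from Objective 2.

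Fourth, a paired table alone does not isolate a compassion-specific response. Labelling people who are negative on CFI and not on relaxation keeps two cut-offs: −5.1 and −4.9 ms would count as specific, −20 and −5 ms would not. With no task effect that label still catches 2.4 to 3.9 of 25 people, and 4.2 under the common shift. This is why the fix also uses the direct change.

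Finally, the study is exploratory, small, and has self-reported affect as a second source of evidence. That limits the consequences but does not supply the missing definition.

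**Conclusion.** The point holds for the individual-level HRV responder analysis. The reference task and sign are undefined, and separate counts cannot show who responds negatively to compassion specifically or how precise the trial 1 comparison is. The bound of 0 to 8 compassion-only negatives, given 8 on each task among 25, needs no assumption. The 39% to 58% overlap does: control as reference, SD 5 to 15 ms, correlation 0.5, no task effect.

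A reader might attribute all of that overlap to the shared control reading. The figures do not support this, since 16% to 37% would overlap with independent differences. Nor do the documents show that the HRV conclusions as a whole are invalid. The group-level tests are unaffected, and the loss is in what the counts can be taken to mean. The change should be made before analysis, so that the reference task is not chosen with the results in view.

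**What to change.** In the Data analysis section:

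1. Score each imagery task against the same session's control task, and state that a fall in RMSSD of at least 5 ms is negative and a rise of at least 5 ms is positive.
2. For trial 1, report the within-person 3 x 3 table of CFI response (negative, neutral, positive) by relaxation response. Compare negative on CFI only with negative on relaxation only by an exact McNemar test or interval.
3. Report the within-person CFI − relaxation change in RMSSD, with the same 5 ms threshold, as the measure of a compassion-specific response. Show where these participants fall in the 3 x 3 table, so that someone above control in both tasks is visible.
4. Describe participants negative on both tasks separately, and do not take the CFI-versus-control count alone as evidence of compassion-specific threat.

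The cost is a few sentences and one extra table from data already recorded. Where imagery in general lowers RMSSD, fewer participants will be described as having a compassion-specific negative response. The change does not remove threshold noise or the effect of the fixed task order, and the report should say so.

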### **SPECIFIC OBJECTIVES**

1. How do clinical participants initially respond to *self*-compassionate imagery in an initial trial, compared to relaxation and a control task? (using self-report and HRV measures)
2. Do any threat responses reduce following repeated trials of self-compassionate imagery?

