### Design:

Participants will be randomized to complete 3 or 4 trials (see details below) using a 2:1 ratio, using a randomization sequence drawn up prior to the study start. This will allow us to explore in a small subgroup whether a fourth trial impacts results. We are also running a related study, which will explore the effects of psychotherapy that will be offered following these 3-4 trials, and we anticipate that a fourth trial will increase probability of dropout from the second study, therefore we will not assign all participants to do the fourth trial.

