#### Procedure

Participants will complete an initial screening questionnaire online including: an informed consent (see Appendix 1), demographics questions, ODSIS, OASIS and FSCRS. Eligible participants will be invited to attend in-person sessions. In each session, HRV will be measured by a research assistant whilst the participant engages in three 4-minute tasks in the following order:

- **Control task:** participants will read a magazine with neutral content for 4 minutes
- **Relaxation imagery** (see appendix 3): participants will complete a relaxation exercise of beach or forest imagery for 4 minutes.
- **Compassion-focused imagery:** participants will complete a compassion-focused imagery for 4 minutes (see appendix 3).

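### For Objective 2, no planned analysis sets the change over trials in the compassion response against the change in the relaxation response, so general familiarity with imagery or the sessions could be read as an effect of repeating compassion imagery

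*Combined protocol and SAP*

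**What the plan says.** Under Specific Objectives, Objective 2 asks: "Do any threat responses reduce following repeated trials of self-compassionate imagery". It names no comparator task. Objective 1 does, but for the first trial only: "imagery in an initial trial, compared to relaxation and a control task". The executive summary says why relaxation is in the design: "to control for certain task demands but without the compassion element".

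The Procedure section repeats all tasks at every visit, in one fixed order (control, relaxation, CFI): "In each session, HRV will be measured by a research assistant whilst the participant engages in three 4-minute tasks". The Design section randomises only the number of trials: "Participants will be randomized to complete 3 or 4 trials (see details below) using a 2:1 ratio". Everyone therefore does the same three tasks in Trials 1 to 3, and nobody attends repeated sessions without CFI.

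Data analysis has these outputs that bear on change over trials:

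- Affect: a paired t-test, "iii) to explore whether changes in positive and negative affect during CFI are greater or smaller from Trial 1 to Trial 3". No affect analysis is planned for relaxation or control.
- HRV, group level: paired t-tests between the three tasks, with no trial named and no task-by-trial contrast.
- HRV, individual level: a response is a change of at least 5 ms in RMSSD between two tasks in one person. Positive and negative responses are counted for relaxation and for compassion in each trial. The counts serve to compare compassion with relaxation at Trial 1 and, across trials, to "ii) explore whether repeated trials improved response to each task".

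**The concern.** Over three sessions participants repeat CFI, but they also repeat relaxation imagery and magazine reading, and they grow used to the electrodes, the assistant and the setting. The Measures section predicts threat responses in some participants at the start and relaxed or neutral responses in all after 3 to 4 trials. Growing ease with imagery in general, or with the sessions, would produce the same pattern.

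Relaxation is the design's own control for what is not specific to compassion. The plan uses it in that role at Trial 1 but specifies no such comparison for change over trials. Because neither randomised group omits CFI, the comparison between tasks within a session is the only control for time available in Trials 1 to 3. What is at stake is how a fall in threat responses can be interpreted under Objective 2. The task comparison at Trial 1 is a separate matter.

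**Working it through.** The plan has no figure to reproduce here: "We plan to recruit a sample of 25 participants for this study" rests on similar earlier studies, with no SD, effect size or alpha. The inputs below other than n = 25 and the 5 ms threshold are assumptions, including the two-sided 5% level.

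**1. Affect test, CFI only.** Let d be a non-specific shift from Trial 1 to Trial 3 in the pre-post affect response, in SDs of the paired difference, with no compassion-specific effect. The paired t statistic has 24 degrees of freedom and noncentrality d × √25 = 5d.

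| d (assumed) | noncentrality | CFI-only test significant |
|---|---|---|
| 0.3 | 1.5 | 30% |
| 0.5 | 2.5 | 67% |
| 0.7 | 3.5 | 92% |

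If relaxation shifts by the same amount, the CFI change minus the relaxation change has mean zero. In simulation it was significant in about 5% of studies, at between-task correlations of 0 and 0.5.

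**2. HRV counts, control as the reference task.** Assume a within-task SD of 6 ms. The compassion-minus-control difference then has SD 6 × √2 = 8.49 ms.

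- No shift: the probability of a positive response is P(Z ≥ 5/8.49) = P(Z ≥ 0.59) = 28%. By symmetry, a negative response has 28%.
- A shift of 5 or 10 ms in all three tasks cancels from the difference: 28% and 28% again.
- A shift of 5 ms in the imagery tasks only: positive P(Z ≥ 0) = 50%; negative P(Z ≤ −10/8.49) = 12%.
- A shift of 10 ms in the imagery tasks only: positive P(Z ≥ −5/8.49) = 72%; negative P(Z ≤ −15/8.49) = 4%.

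So counts against control remove general familiarity with the sessions, provided it acts equally on all tasks. They do not separate practice with imagery from practice with compassion.

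**3. The missing contrast.** For RMSSD it is (CFI − relaxation) at Trial 3 minus (CFI − relaxation) at Trial 1, within person. A shift shared by the imagery tasks drops out. So does an effect of the fixed task order, as long as that effect is the same in each session.

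**4. Its precision.** With n = 25 and 80% power, a paired t-test detects 0.584 SD of the quantity tested. If the Trial 1 to Trial 3 changes in two tasks have equal SDs and correlation ρ, their difference has SD √(2(1 − ρ)) times the within-task SD:

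- ρ = 0: 0.584 × 1.414 = 0.83 SD
- ρ = 0.5: 0.584 × 1.000 = 0.58 SD
- ρ = 0.7: 0.584 × 0.775 = 0.45 SD

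The CFI-only test detects 0.58 SD. The contrast is therefore less precise below ρ = 0.5 and no worse above it.

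**The case against.** Several points on the other side stand.

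- A reader might infer that the plan never relates CFI to another task over time and cannot tell habituation from a CFI effect. For HRV the documents do not support that. A response is defined between two tasks, and relaxation counts appear beside compassion counts in each trial, so a parallel improvement would be visible. If the reference is control, the counts are a dichotomised form of one of the contrasts recommended here. But the reference is unnamed, no test is attached to the counts, and nothing formally compares the two changes.
- The affect score is a pre-to-post change, so a shift in the level of the whole session largely cancels. Only a change in reactivity to the task would bias test (iii).
- The 30%, 67% and 92% are the ordinary power of any paired t-test with 25 pairs. They place the assumed shift on the response itself, and the 5% follows from assuming an equal shift in both tasks. They illustrate the affect test and say nothing about the HRV counts.
- The proposed contrast does not settle specificity. If CFI starts with more threat responses than relaxation, it has more room to fall, through habituation or regression to the mean.
- The study is small and exploratory. That limits the weight of the point, but the result will still be interpreted, and the RMSSD contrast needs no new data.

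**Conclusion.** The point holds in limited form. For affect, Objective 2 has no comparator across trials. For HRV, the counts are relative to an unnamed task, and compassion is set against relaxation only at Trial 1. No specified analysis asks whether the compassion response changed more than the relaxation response.

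A reader might also infer that the plan commits itself to crediting repeated compassion imagery with any improvement. It does not: Objective 2 asks what happens after repeated trials, and the analyses are described as exploring. The risk lies in how the results could be read.

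The size is uncertain because the documents give no habituation figure, SD or between-task correlation. Under the assumed shifts, the affect test would be significant without any specific effect in 30% to 92% of studies. HRV counts against control would be unaffected by a shift common to all tasks, but clearly moved by one confined to imagery. This is an inexpensive improvement to the plan, not a flaw that invalidates the study.

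**What to change.** 1. Name the reference task for the 5 ms RMSSD response, for relaxation and for compassion.
2. Add two within-person contrasts for Objective 2: the Trial 1 to Trial 3 change in RMSSD for CFI minus relaxation, and for CFI minus control, each by paired t-test with a confidence interval.
3. Report the CFI-only affect test (iii) as change over sessions, not as an effect specific to compassion imagery. A specific claim would need affect rated around relaxation too, and the same contrast applied to it.
4. State that a larger change in CFI than in relaxation is supportive, not conclusive, because the two tasks may start from different levels of threat response.

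Items 1, 2 and 4 and the reporting limit in item 3 change only the wording of the plan, since RMSSD is to be recorded for all three tasks in every session. The extra affect ratings would change the procedure and are optional. The statistical cost is precision: unless the changes in the two tasks correlate at 0.5 or more, the contrast is noisier than the CFI-only change, so a wide interval should not be read as showing no specific effect.
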